# 2 INTRODUCTION

## 2.1 Vaginal and Oral Interventions to Control the Epidemic (VOICE)

The VOICE Study will simultaneously assess the safety and efficacy of daily dose oral and vaginal formulations of tenofovir (TDF) and oral FTC/TDF in preventing HIV acquisition. The study design of VOICE also allows limited comparisons of effectiveness, safety, adherence, and associated frequency of viral resistance among HIV seroconverters across formulations.

VOICE is a Phase 2B, five-arm, multi-site, randomized, placebo-controlled trial that is double-blinded within each mode of administration, but open-label with respect to the randomly assigned mode of administration (vaginal or oral). Approximately 5000 participants will be randomized to the five study arms in a 1:1:1:1:1 ratio.

While investigators and participants will be aware of randomization to either the oral or vaginal administration of study product, they will be blinded to the specific study products randomly assigned. All participants will complete monthly follow-up visits for a period of 12 to 36 months, and will receive ongoing HIV risk reduction counseling, condoms, and diagnosis and treatment of sexually transmitted infections (STIs) throughout the course of study participation. Participants will also be scheduled for a Termination Visit approximately 8 weeks following completion of their scheduled end-of-study product use.

The BMD Substudy will explore the potential effects of oral study products on BMD in a subset of VOICE participants.

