## Secondary Objectives:

- To describe changes over time in nutritional assessment components among VOICE participants receiving oral study products.
- To compare changes in BMD over the duration of the BMD Substudy among participants receiving oral TDF and FTC/TDF compared with placebo.
- To evaluate changes in BMD in the 12 months following the discontinuation of an oral study product in VOICE.

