#### 4.5 Study Groups

The three study groups included in the BMD Substudy are as follows:

- TDF group (TDF 300 mg and FTC/TDF placebo)
- FTC/TDF group (TDF placebo and FTC/TDF 200 mg/300 mg)
- Oral placebo group (TDF placebo and FTC/TDF placebo)

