## 10.5 Data and Safety Monitoring and Analysis

When the use of descriptive statistics to assess group or site characteristics or differences is required, the following methods will be used: for categorical variables, the number and percent in each category; for continuous variables, the mean, median, standard deviation, quartiles and range (minimum, maximum). To assess the differences between the three oral arms, participants will be compared for baseline characteristics including demographics using descriptive statistics.

For the primary analysis, two Student t-tests will be used to compare the percentage reduction after one year of follow-up in BMD between each of the following: (1) the TDF active arm and placebo oral arm; and, (2) FTC/TDF active arm and placebo oral arm. Analysis for hip and lumbar spine measurements will be done separately.

BMD hip and lumbar assessments are done every 6 months, but a substantial number of women will have terminated the VOICE trial before reaching their year-2 BMD assessments. Assuming uniform recruitment over 21 months, about 130 of the 300 women will have a year-2 BMD assessment. This reduction in participant numbers will result in a reduction of the statistical power in comparison to that observed following year-1. However, to explore possible trends over the entire follow-up time, GEE models for repeated measures will be used where BMD from all time points are included in the analysis. Similar methods will be used to compare changes after one/two year(s) of follow-up in bone turnover, bone mineral metabolism, and nutritional assessment components. Distribution of some of these endpoints may not allow the use of the Student t-test (e.g., height is expected to have very little variation over a year), in which case a McNemar's test approach might be used, or the proportion of women with an observed percentage change might be compared across arms using a Fisher exact test.

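### McNemar's test is named as one of two stand-ins for the between-arm t-test on secondary and exploratory endpoints, but as a paired within-woman test it cannot compare the randomized arms

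*Protocol*

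**What the plan says.** Protocol Section 10.5 sets the primary analysis as two Student t-tests on percentage change in BMD, between "1) the TDF active arm and placebo oral arm; and, (2) FTC/TDF active arm and placebo oral arm". After describing the GEE models for all time points, it turns to the other endpoints: "Similar methods will be used to compare changes after one/two year(s) of follow-up in bone turnover, bone mineral metabolism, and nutritional assessment components". It then allows for exceptions: "Distribution of some of these endpoints may not allow the use of the Student t-test", with height as the example because it should hardly vary over a year. For such endpoints the text continues: "in which case a McNemar's test approach might be used, or the proportion of women with an observed percentage change might be compared" across arms, and it names the Fisher exact test for that second option.

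Section 2.1 describes the parent trial's allocation: "Approximately 5000 participants will be randomized to the five study arms in a 1:1:1:1:1 ratio". Section 4.5 lists three parallel oral groups. No section describes matching women across groups.

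Section 3 words the nutritional secondary objective as description: "To describe changes over time in nutritional assessment components among VOICE participants receiving oral study products".

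**The concern.** A fallback for a t-test should answer the t-test's question. Here that question is whether change on TDF, or on FTC/TDF, differs from change on placebo. McNemar's test takes pairs of yes/no values and asks whether switches in one direction outnumber switches in the other. With the same woman measured twice, that is a question about time within a group, and the placebo arm does not enter. The example given, height, is also continuous, so it would have to be reduced to a category at each visit before the test could be run at all.

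The two fallbacks are joined by *or*, as if interchangeable. If an analyst took the first for an arm comparison, a change common to all arms could be reported as though it bore on the products, and a difference between arms could go unseen. The marker results are meant to help explain any BMD loss (Sections 2.4 and 3), and for that purpose the contrast with placebo is the one that matters.

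**Working it through.** **1. The plan's own figure.** Section 10.4 gives SD 4.5%, difference 2.1%, two-sided 5% error, 90% power and 100 women per arm.
- n per arm = 2 × SD² × (1.960 + 1.282)² / difference² = 2 × 20.25 × 10.51 / 4.41 = 96.5, so 97.
- Power with 100 per arm is 0.910 (normal) or 0.907 (t). The smallest difference detectable with 90% power is 2.06% (normal) or 2.07% (t).

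The stated figure reproduces. It concerns the primary BMD t-test, which this point does not touch. The protocol states no figure for either fallback.

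**2. What each test uses.** In one arm, let u be the number of women who switch upwards between visits and d the number who switch downwards.
- McNemar's statistic is (d − u)² / (u + d). It contains no count from another arm.
- The Fisher test sets d out of n in the active arm against d out of n in placebo.

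**3. Two worked tables with 100 women per arm.** The switching rates are assumptions, because the documents give none.
- *Same shift in both arms:* u = 5 and d = 20 in each. McNemar in the active arm: (20 − 5)² / 25 = 9.0 on 1 degree of freedom, p = 0.003 (exact p = 0.004). Fisher on 20/100 against 20/100: p = 1.0.
- *Arms differ in the proportion who decrease:* active u = 15 and d = 15, placebo u = 2 and d = 2. McNemar in the active arm: (15 − 15)² / 30 = 0, p = 1.0. Fisher on 15/100 against 2/100: p = 0.0015.

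**4. Rejection rates.** Simulation, 3,000 runs, 100 per arm, two-sided 5%, exact McNemar in the active arm against Fisher between arms:

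| Assumed true rates (up/down) | McNemar within active arm | Fisher between arms |
|---|---|---|
| 5%/20% in both arms | 83.8% | 3.8% |
| 10%/10% in both arms | 2.6% | 3.3% |
| 5%/25% active, 5%/5% placebo | 95.6% | 97.5% |
| 15%/15% active, 2%/2% placebo | 3.0% | 91.8% |

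The tests agree in rows 2 and 3, where placebo has no net shift and any arm difference appears as a net shift on active. They part in rows 1 and 4. Row 1 is a change over time with no arm effect; row 4 is an arm effect with no net change over time.

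**5. Could women be paired across arms?** Pairing each active woman with an arbitrary placebo woman makes McNemar computable between arms. In the same simulation this rejected in 3.5% of runs for row 1 and 91.2% for row 4, close to Fisher. But its result depends on an arbitrary pairing, it gains nothing over Fisher, and the protocol describes no such pairing.

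**The case against.** The strongest reply is that the protocol may intend McNemar's test only for change within women. The nutritional objective is descriptive, height is a nutritional component, and the phrase about comparing across arms is attached only to the Fisher option. A paired test on a before/after category would serve that objective. This stands as a possible reading, and it is why restricting the test is as good a remedy as deleting it. The text does not state that restriction, however. It introduces McNemar's test where the Student t-test cannot be used, and the only t-tests the section defines compare arms.

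It can also be said that the wording is permissive, that a valid between-arm test stands in the same sentence, and that under Section 7.5 stored specimens may be assayed only if significant BMD changes are seen, so marker comparisons may never be run. All of this is true and keeps the point small.

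Nor is this a matter to leave to an analysis plan. The objection is not to missing detail but to a method the protocol itself names.

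A reader might go further and infer that arms will be compared by setting a significant within-arm result against a non-significant one, and attach a false-positive rate to that. The protocol describes no such procedure, so no rate of that kind can be charged to it. A reader might also object that the Fisher option discards information by cutting a continuous change into a proportion. That is a preference rather than an error. For height, where most women may show no change, a proportion is a reasonable summary and a rank test would be dominated by ties.

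**Conclusion.** The point holds in a limited form. Section 10.5 names, as one of two possible substitutes for a comparison of independent arms, a paired binary test that cannot make that comparison. The other substitute, the Fisher exact test across arms, can.

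It is a minor correction. It concerns secondary and exploratory endpoints whose distribution does not suit the t-test, and the protocol does not say which of these, beyond height, would qualify. The primary BMD analysis, its power and the BMD comparison after product discontinuation are unaffected.

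The conclusion rests on what the test measures and on the absence of any matching across arms. The percentages in the simulation table depend on assumed switching rates; they show how the two tests can disagree and do not estimate harm in this study. It would be too strong to say that McNemar's test is the only fallback, or that the mechanism and nutrition results will lack a valid comparison with placebo. The sentence itself provides a valid one.

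**What to change.** Amend the one sentence in Section 10.5:
- Delete McNemar's test from the arm comparison, or state that it is used only to describe within-arm change in binary before/after findings.
- For each active arm against placebo, where the t-test is unsuitable, use the Fisher exact test already named, or a rank-sum test for skewed continuous changes. For height, the Fisher comparison of proportions can stay.

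The cost is an edit to one sentence. No procedure, visit, data collection or sample size changes.

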#### Bone turnover

Previous investigators have demonstrated that high bone turnover is an independent risk factor for hip fractures in older women. Although it is unlikely that young women will experience fractures, they may experience bone loss, a major endpoint in the substudy. Greenspan and others have previously demonstrated that bone turnover (bone resorption coupled with bone formation) is associated with the rate of bone loss in women.  Markers of bone resorption include CTX (C-terminal telopeptide of type 1 collagen). Markers of bone formation/growth include P1NP (N-propeptide of type 1 collagen) and BSAP (bone-specific alkaline phosphatase). The major objective of the substudy is to examine potential changes in bone mass in women taking the oral study drugs. If there are significant decreases in BMD, it will be important to determine whether this is due to an increase in bone resorption (increase in CTX), a decrease in bone formation (decreased P1NP and BSAP), or possibly an increase in all markers characterized by greater resorption than formation, leading to the loss of bone.

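### McNemar's test is offered as an optional fallback for comparing change between arms in secondary and exploratory endpoints, which a paired within-woman test cannot do (low priority)

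*Protocol*

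**What the plan says.** Section 10.5 first sets the primary BMD analysis: "two Student t-tests will be used to compare the percentage reduction after one year of follow-up in BMD between each of the following", followed by TDF against placebo and FTC/TDF against placebo. It adds GEE models for the whole follow-up. It then carries these methods over to the other endpoints: "Similar methods will be used to compare changes after one/two year(s) of follow-up in bone turnover, bone mineral metabolism, and nutritional assessment components".

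The fallback follows directly. "Distribution of some of these endpoints may not allow the use of the Student t-test", with height as the example because it should hardly vary over a year, "in which case a McNemar's test approach might be used". The same sentence gives a second option: "the proportion of women with an observed percentage change might be compared across arms using a Fisher exact test".

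Two other places matter. Section 4.5 opens "The three study groups included in the BMD Substudy are as follows" and lists TDF, FTC/TDF and oral placebo. These are parallel groups of different women, and no matching across arms is described. In Section 3 the nutrition objective is "To describe changes over time in nutritional assessment components among VOICE participants receiving oral study products", which is descriptive.

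**The concern.** The fallback stands in for a two-sample comparison of each active arm with placebo. McNemar's test uses one yes/no variable measured twice in the same women and looks only at those whose status changed. Run within an active arm, it tests whether prevalence in that arm moved over time. Placebo does not enter, so the result cannot separate a product effect from a trend common to all arms. The variable must also be yes/no, whereas the protocol's example, height, is continuous and no cut-off is named.

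What is at stake is interpretation of the supporting endpoints. Section 2.4 says of a BMD decrease that "it will be important to determine whether this is due to an increase in bone resorption" or to reduced formation. Attributing such changes to product needs the placebo arm.

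**Working it through.** **The plan's own figure.** Section 10.4 assumes an SD of 4.5% and 100 women per arm, and states a detectable difference of 2.1% at 90% power and 5% type one error. Detectable difference = SD × √(2/n) × (1.960 + 1.282) = 4.5 × √(2/100) × 3.242 = 2.06%. Power at 2.1% is 0.91. The figure reproduces, but it concerns the BMD t-tests and does not bear on this point. The protocol gives no figure for the fallback.

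**What each method compares** (Section 10.5 set against Section 4.5):
- t-test of each active arm against placebo: different women, and placebo is in the test.
- Fisher exact test across arms: different women, and placebo is in the test.
- McNemar's test: the same women at two times, with no placebo in the test.

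**Inputs for the size.** 100 women per arm is from Section 10.4. The shares of women crossing a cut-off up (u) or down (d) are assumptions, because the protocol gives none. Both arms receive the same u and d, so there is no product effect.

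**Formulas.** With b women crossing up and c crossing down in an arm, McNemar's test is a two-sided binomial test of b out of b + c against one half. In large samples this is (b − c)²/(b + c), compared with 3.84. At the expected counts:
- 20%/8%: (20 − 8)²/28 = 5.14
- 18%/10%: (18 − 10)²/28 = 2.29
- 4%/1%: (4 − 1)²/5 = 1.80
- 2%/1%: (2 − 1)²/3 = 0.33

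The exact test also needs at least six crossings to reach 5%: five in one direction give 2 × 0.5⁵ = 0.0625, and six give 2 × 0.5⁶ = 0.031. That is why it rarely rejects when few women cross.

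**Results.** McNemar figures are from the exact binomial test with n = 100. The two-sample column is a simulated z-test on change scored −1, 0 or +1. The chance that exactly one of two arms is significant is 2p(1 − p), where p is the McNemar rejection rate.

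| u / d, same in both arms | McNemar within one arm (p) | Exactly one of two arms significant | Two-sample test |
|---|---|---|---|
| 2% / 1% | 0.6% | 2 × 0.006 × 0.994 = 1% | about 5% |
| 3% / 1% | 3.5% | 2 × 0.035 × 0.965 = 7% | about 5% |
| 4% / 1% | about 10% | 2 × 0.10 × 0.90 = 18% | about 5% |
| 18% / 10% | about 26% | 2 × 0.26 × 0.74 = 38% | about 5% |
| 20% / 8% | about 56% | 2 × 0.56 × 0.44 = 49% | about 5% |

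With no trend (5%/5%) McNemar's test rejects in about 2%. The excess therefore comes from the shared trend, not from a faulty test level. A separate run at 10%/5%, 15%/5%, 20%/10% and 20%/5% gave within-arm rejection of 17%, 54%, 38% and 84%. Fisher's exact test between arms, on the share crossing up, rejected in about 3% throughout.

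**The case against.** The strongest reply is that nothing is fixed. The wording is conditional, and the same sentence supplies a valid between-arm test. The phrase about comparing across arms is attached to Fisher's test only, so a fair reader may take McNemar's test as meant for change over time and Fisher's for the arm comparison. The nutrition objective, which covers the height example, is descriptive, and a within-woman test can serve it. The choice between fallbacks could be settled in an analysis plan that is not shown.

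Much of this stands, and it sets the priority. It does not remove the point. Section 10.5 introduces the whole passage as comparing changes by methods similar to the active-versus-placebo analysis. It covers bone markers as well as nutrition, and it gives no rule for choosing between the two options. A test named for a comparison it cannot make is a misstatement, not a detail left for later.

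Three stronger readings are tempting, and the documents do not support them:
- A reader might infer that a false product signal is likely in the protocol's own example. Height is expected to change very little, so few women would cross a cut-off, and the low rows of the table are the relevant ones.
- A reader might infer that active and placebo women would be pooled, so that opposite movements cancel. No section proposes pooling.
- A reader might argue that young age, DMPA and breastfeeding make shared trends, and so false signals, probable. Sections 2.2.1 and 2.4 discuss these in relation to BMD, which is analysed by between-arm t-tests and GEE. Section 7.5 adds that stored samples may be assayed if significant BMD changes are seen, and nothing says that the markers would trigger the fallback.

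**Conclusion.** The point holds in a limited form. McNemar's test cannot compare independent arms, and Section 10.5 offers it as one optional substitute for a test that does. If it were run within an active arm and read as a product effect, a trend shared with placebo would be flagged in about 1% to 10% of trials with few crossings and in about 26% to 56% at 18%/10% to 20%/8%, against about 5% for a two-sample test. These figures rest on 100 women per arm and on assumed crossing rates.

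Only secondary and exploratory endpoints are exposed. The primary BMD comparisons, the sample size and the Fisher option are unaffected. It would go too far to conclude that the protocol commits to an invalid analysis. Low priority.

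**What to change.** In Section 10.5, remove McNemar's test as an option for comparing arms, or state that it serves only to describe change over time within an arm. Add that, where the t-test does not suit, each active arm is compared with placebo by a two-sample method. Examples are a rank-sum test on continuous change such as height, or the Fisher exact test already named for a yes/no outcome. Other two-sample methods would do equally well. What matters is that placebo enters the test.

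The cost is one sentence in the protocol or the analysis plan, with no extra data, participants or visits.

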## Bone Mineral Density Changes Over Time

Two studies have reported on the changes in bone mineral density in healthy HIV negative adult men. In both the iPrEx and CDC MSM PrEP studies, healthy men taking tenofovir DF 300 mg daily had a statistically significant loss of bone mineral density of approximately 1% after 24 to 48 weeks compared to placebo. In the iPrEx study, 503 geographically diverse (5 countries) men participated in the BMD substudy. The loss of bone mineral density among participants in the FTC/TDF arm of the iPrEx study was not associated with any clinical harm, as the FTC/TDF (247 randomized to FTC/TDF) and placebo (256 randomized to placebo) participants reported comparable rates of bone fractures. Although these results are reassuring it is important to closely examine the effect of tenofovir in HIV-negative women, who, as previously stated, are exposed to the differential effects on bone density of contraception, breastfeeding, pregnancy, etc., all known to impact bone mineral density.

Limited data suggest that the bone mineral density changes related to tenofovir are reversible after discontinuation of drug in HIV-positive individuals. This has not been studied in HIV-uninfected persons and is critical information for determining the long term effect of a period of oral PrEP, especially for women. MTN-003B is well structured to obtain BMD data after study drug discontinuation, and to compare changes among active drug and placebo participants.

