## 7.3 Follow-up Visits

Follow-up visits will occur on a semiannual basis (approximately every 6 months) and may be completed on the same day as VOICE Study visits. The follow-up visits will occur at 6 months and 12 months following the VOICE PUEV. The semiannual follow-up visit procedures listed below will also be completed at either the VOICE PUEV or the BMD Substudy ETV if at least 30 days have passed since the last semiannual follow-up visit.

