At each assessment time point during the expected product use period, the arithmetic mean of the duplicate measurements will be used for the following primary analysis. Two Student t-tests (two-sided) will be used to compare the percentage reduction in BMD between the TDF active arm, FTC/TDF active arm, and placebo arm. Analyses for hip and lumbar spine measurements will be done separately. Based on the above SD estimates, a sample size of 100 women per oral arm allows the detection of a difference as small as 2.1% with 90% power with a type one error rate of 5%. Note that this is a conservative estimate of power since the duplication of measurements at each time point will reduce the SD and thus provide power to detect lower differences (i.e., <2.1%). However, the reduction in SD is difficult to quantify since no data are currently available on the measurement error that could be anticipated at each of the proposed sites.

Similarly, the percentage change in BMD between the TDF active arm, FTC/TDF active arm, and placebo arm observed during the year after product use was discontinued will be compared. Based on similar assumptions as above, 100 women per oral arms will allow the detection of a difference as small as 2.1% with 90% power with a type one error rate of 5%.

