For evaluating changes in BMD after product use was discontinued, two Student t-tests will be used to compare the percentage change over the year of follow-up without product use in BMD between each of the following: (1) the TDF active arm and placebo oral arm; and, (2) FTC/TDF active arm and placebo oral arm. Analysis for hip and lumbar spine measurements will be done separately. Note that this analysis is more relevant in the case where at least one effect from the use the active oral products on BMD is observed. In that case, it would be worthwhile to investigate if the effect on the BMD is waning after product use is discontinued and eventually returns to its baseline values (i.e. prior to initiation of product use).

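### The off-product t-tests can show whether a BMD effect is waning, but not whether BMD returns to its pre-product value, and no contrast is assigned to that question

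*Protocol*

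**What the plan says.** The secondary objective in section 3 is "To evaluate changes in BMD in the 12 months following the discontinuation of an oral study product in VOICE". For this, section 10.5 plans that "two Student t-tests will be used to compare the percentage change over the year of follow-up without product use in BMD", comparing TDF with placebo and FTC/TDF with placebo, with hip and spine analysed separately. Section 10.4 powers the same window: percentage changes "observed during the year after product use was discontinued will be compared", with 100 women per arm, a 2.1% difference, 90% power and 5% type I error.

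Section 10.5 then explains when and why the result matters. It says "this analysis is more relevant in the case where at least one effect from the use the active oral products on BMD is observed", and that in this case one would want to "investigate if the effect on the BMD is waning after product use is discontinued and eventually returns to its baseline values". A parenthesis defines baseline as the value before product use began.

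On timing, section 7.3 states: "The follow-up visits will occur at 6 months and 12 months following the VOICE PUEV". DXA is done at enrolment, at each semiannual visit, and at PUEV if at least 30 days have passed since the last semiannual visit (section 7.3 and Table 1).

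Section 2.4 explains the importance. Reversibility is unstudied in HIV-uninfected people and is "critical information for determining the long term effect of a period of oral PrEP, especially for women".

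Two other provisions bear on the point. Section 3 has a separate secondary objective on BMD change across the whole substudy, and section 10.5 plans GEE models using BMD at all time points to explore trends.

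**The concern.** Section 10.5 raises two questions: is the effect waning, and does BMD get back to where it started? A difference in change over the off-product year answers the first. It cannot answer the second, because the enrolment value does not enter the statistic. Two arms that stay flat after PUEV look identical, whether or not one of them entered that year with a deficit.

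At stake is the conclusion on reversibility. If the off-product comparison is reported alone, a null result cannot be told apart from a lasting loss. A significant regain could also be taken as complete recovery when it is only partial.

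**Working it through.** **Inputs.** From section 10.4: 100 women per arm, SD of percentage change 4.5% (range in the text 3.5% to 5.5%), type I error 5%, detectable difference 2.1%, power 90%. Two-sided testing is stated for the primary t-tests, and the off-product comparison is described as similar. From section 2.4: a loss of about 1% against placebo in HIV-negative men. Assumed, because the documents do not give them: a stable placebo mean, and an SD of 4.5% also over the longer span from enrolment to the last visit.

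**The plan's own figure.** The standard error of a between-arm difference is 4.5 × √(2/100) = 0.636. Then 2.1/0.636 = 3.30, and 3.30 − 1.96 = 1.34, which gives power of 0.91 (0.907 with the noncentral t). The required size is 97 per arm. The stated 90% is reproduced, so the power arithmetic is sound. The question is what is being compared.

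**What the statistic contains.** Let D_on be the arm-versus-placebo difference in percentage change from enrolment to PUEV, and D_off the difference from PUEV to 12 months later. To a close approximation, the net difference from enrolment is D_net = D_on + D_off. The t-tests estimate D_off, and return to baseline is a statement about D_net. With D_on = −2:

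- no recovery: D_off = 0, D_net = −2
- half recovery: D_off ≈ 1 (0.99/0.98 − 1 = 1.02%), D_net = −1
- full recovery: D_off ≈ 2 (1/0.98 − 1 = 2.04%), D_net = 0

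**How the tests behave.** Each row is 20,000 simulated trials, 100 per arm, SD 4.5%, two-sided 5%.

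| Loss at PUEV | Recovery | Mean off-product difference | Residual against enrolment | Off-product test rejects | Enrolment-based test rejects |
|---|---|---|---|---|---|
| none | n/a | 0.00 | 0.00 | 5% | 5% |
| 1.0% | 0% | 0.00 | −1.00 | 5% | 35% |
| 1.0% | 50% | 0.51 | −0.50 | 12% | 12% |
| 1.0% | 100% | 1.01 | 0.00 | 35% | 5% |
| 2.1% | 0% | 0.00 | −2.10 | 5% | 91% |
| 2.1% | 50% | 1.07 | −1.05 | 39% | 38% |
| 2.1% | 100% | 2.15 | 0.00 | 92% | 5% |

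In the off-product column, no effect and a permanent deficit of either size all give 5%. The enrolment-based column separates them, but it has the opposite weakness: a permanent 1.0% deficit is missed about 65% of the time (exact t power 52% at SD 3.5%, 35% at 4.5%, 25% at 5.5%).

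**Why an interval is needed.** The 95% half-width for D_net is about 1.97 × 0.636 = 1.25 points (0.98 at SD 3.5%, 1.53 at SD 5.5%). An estimate of zero would therefore still be compatible with a residual deficit of about 1.25 points, which exceeds the roughly 1% loss cited in section 2.4. A non-significant enrolment-based test is not proof of return either.

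**The case against.** The other side has several good points. The secondary objective asks only for an evaluation of changes in the 12 months after discontinuation, and the t-tests match that wording. The return-to-baseline remark is conditional on an on-product effect and reads as a further investigation. It is not a claim that the t-tests settle the matter. The separate objective on change over the whole substudy, whose follow-up runs to 12 months after PUEV, together with the GEE over all time points, could yield the residual difference at the last visit. Model terms are normally left to a statistical analysis plan, which is not at hand.

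Most of this stands, and it rules out three stronger readings that a reader might infer. The first is that the trial cannot assess reversibility. It can, because the scans and a suitable class of model are both planned. The second is that the GEE is unsuitable because it pools on- and off-product scans. That presumes a model without time or period terms, which the protocol does not say. The third is that the protocol takes no difference between arms as reassurance. It nowhere reads a null result as reversal, and since it ties the analysis to a prior on-product effect, a careful reader would take a null as no waning shown.

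What the objection does not remove is narrower. Section 10.5 names return to pre-product values as the matter of interest, fixes one statistic beside it that cannot address it, and assigns no other contrast to it. Combining the off-product result with the year-1 primary result does not fill the gap, because VOICE follow-up runs 12 to 36 months (section 2.1). For women who stay on product longer, the year-1 difference is not the difference at PUEV.

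**Conclusion.** The point holds in this limited form. The off-product t-tests are a proper measure of waning and fit the literal secondary objective, but they do not address return to the pre-product value. For a 2% excess loss at PUEV, off-product differences of about 0, 1 and 2 points correspond to residual deficits of 2, 1 and 0 points. The expected off-product difference is zero under a permanent deficit of any size, just as it is under no effect.

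The zero follows from how the statistic is defined and does not depend on the SD. The rejection rates rest on 100 per arm, SD 4.5% over both spans and a stable placebo mean. Two readings of the text are also involved. PUEV as the reference for the off-product change is inferred from the off-product window and the visit schedule, since section 10.5 does not name it. The enrolment scan, allowed up to 13 days after random assignment, stands in for the pre-product value. The matter concerns a secondary objective and is worth correcting because the correction is cheap.

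**What to change.** In section 10.5:

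- Keep the two off-product t-tests as the measure of waning.
- Add, for each active arm against placebo at hip and at spine, the difference in percentage change from enrolment to 12 months after PUEV, with a 95% confidence interval. A t-test or a contrast from the GEE would serve.
- Report it beside the enrolment-to-PUEV difference, so that loss, regain and residual can be read together. Where PUEV falls within 30 days of the last semiannual visit, that visit's scan supplies the PUEV value.
- State that neither a null off-product difference nor a non-significant enrolment-based test is by itself evidence of reversal. The conclusion rests on the confidence interval for the residual difference.

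The cost is one extra contrast and a few sentences, on DXA data already scheduled. The drawback is that the enrolment-based contrast spans on-product exposure that varies between women, which the report should state.
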